### **Assessment Techniques**

The order of measures will be counterbalanced across subjects to prevent test order effects or systematic effects of fatigue.

*Child and Adolescent Questionnaires (N = 400):* The child and adolescent questionnaire is an extensive survey on psychological, social, and behavioral factors. Construct areas include: demographics; cannabis use behavior and history of cannabis use; cannabis dependence; cannabis motives and expectancies; cannabis withdrawal; current and past use of other substance of abuse (e.g., tobacco, alcohol); family rules about substance use; parental messages about substance use; quality of family communication; peer support; social integration; exposure to risky peer networks; self-esteem; coping; depressive and anxiety symptoms; delinquent behaviors; temperament. The questionnaire is designed to be completed during the protocol visits and is estimated to take approximately 1 hour to complete. Students will be asked to complete this survey in its entirety at the baseline visit. Additionally, certain composite measures that may be sensitive to fluctuations over a 30 day period will also be completed at the remaining seven protocol visits. Such questionnaires may include items relevant to cannabis withdrawal and craving and mood. Questionnaires completed at visits occurring approximately 3, 4, 5, 14, 21, 28, and 56 days following the second baseline will take approximately 20 minutes to complete. If the student prefers, some surveys may be sent electronically via secure REDCap survey links to complete outside of study visits to reduce the length of visits. Participants will have the option to complete all surveys during visits if they choose. Participants will enter data directly into REDCap electronically and will initial and date at the end of each survey to indicate that they inputted this information. In special warranted circumstances, participants will complete questionnaires using pen and paper and study staff will enter the data into REDCap on their behalf.

*Child and Adolescent Interviews (N = 400):* At the first baseline visit, participants will complete a semi-structured interview to assess for current and past psychiatric and substance use disorder diagnoses. At the first baseline, they will also participate in a 20-minute semi-structured time-line follow-back interview. The purpose of this interview is to create retrospectively a calendar of cannabis episodes as well as other

substances of abuse over the previous 90 days. To complete the calendar, MGH staff will work with children and adolescents to identify both the days when they used substances and the substances used on each day. To gather this information, staff will use a modified version of the timeline follow-back procedure that has been successfully used in other studies with child and adolescent substance users. This includes identifying important dates or events that stand out to the participant (e.g., start/end of school, family vacations, parties, dances, etc.). At the second baseline visit as well as visits occurring approximately 3, 4, 5, 14, 21, 28, and 56 days following the second baseline, students will complete this timeline follow-back interview but substance use will only be assessed in the time interval since their previous visit. For children and adolescents who do not use substances and in visits following baseline, this interview will be extremely brief.

**Cognitive Testing (N = 400):** We will focus on changes in verbal learning/memory, attention, working memory, and complex decision-making as some studies show differences in these domains between cannabis users and non-users. Additionally, the neurobiological substrates typically implicated in performance on these tasks (e.g., prefrontal cortex, fronto-subcortical circuitry) undergo the most protracted development during adolescence and may therefore be most susceptible to insults from exogenous cannabinoids. We are proposing to do much of the cognitive testing with the Cambridge Neuropsychological Test Automated Battery (CANTAB). We specifically selected the CANTAB, which is a “state-of-the-art” cognitive battery, based on several criteria to address practical and methodological concerns that may arise from a longitudinal, non-laboratory study. First, the CANTAB has been validated in many populations (including substance using adolescents) and normative data are available. The CANTAB is also administered on a small computerized touch screen tablet, which allows for easy portability, efficient testing of many people (essential for study feasibility), and standardized administration. Third, tests have been adapted from animal model paradigms to increase translatability of findings and tests can be analyzed based on their cognitive components to more readily define impaired and spared cognitive capacities. Next, neuroimaging studies are available that show reliance on neural circuitry implicated in cognitive functioning and addiction. Finally, the CANTAB has been validated longitudinally and offers the unique advantage of parallel forms for retest. The cognitive battery will be administered at the second baseline and visits that are approximately 5, 14, 21, 28, and 56 days following the second baseline.

**Drug Testing (N = 400):** At all study visits, excluding the first baseline visit, participants will provide a urine sample, which will be used qualitatively screen for cannabis use as well as other substances of abuse and quantitatively screen for amount of THC metabolites in urine.

Due to the negative impact that recent outside drug or alcohol use could have on a subject’s performance in the cognitive testing and responses to questionnaires/interviews, subjects in all groups will be asked to refrain from the use of any illicit drugs or the consumption of alcohol within 24 hours of study visits. This short-term abstinence will be assessed using subject self-report at each of the visits involving cognitive testing.

Passive parental consent		Parental/student consent/assent Cannabis users in CM discontinue cannabis use											
		V0	BL Part I (V1)	BL Part II (V2)	V3	V4	V5	V6	V7	V8	V9		
Fitbit Charge 3/Inspire 2		X	X	X	X	X	X	X	X	X	X		
ActiGraph GTX-9												X	
Fitbit ActiGraph Survey											X	X	
Screener	X												
MRI Safety Screen			X										X
Background Questionnaire			X										

Psychopathology Questionnaires										
ADHD—Childhood Sx Checklist		X								
ADHD—Current Sx Checklist			X					X		
Prodromal Questionnaire – PQ-B			X							
MASQ			X		X	X	X	X		
Personality—TIPI		X								
Aggression—BP-AQ		X								
Depression Questionnaire—CES-DC (10-19 yrs, school cohort) – Will be administered at V2 & V8			X					X		
Anxiety Questionnaire—SCARED-R (10-19 yrs, school cohort) – Will be administered at V2 & V8			X					X		
Concise Health Risk Tracking Scale (CHRT)		X	X	X	X	X	X	X	X	
Family Psychiatric History		X								
APSS - Lifetime		X								
APSS - Current		X						X	X	
ERS		X								
Environment Questionnaires										
Family Risk/Protective Factors		X								
Cognition Questionnaires										
Executive Functioning—BRIEF (10-18yrs, school cohort)			X					X		
Executive Functioning—BRIEF (18-25yrs, older adolescent cohort)			X					X		
Delay Discounting—MCQ			X		X			X	X	
Peer Conformity—MISS		X						X		
Impulsivity—UPPS		X								
General SU Questionnaires										
Peer Substance Use/Tolerance		X								
COVID-19 Questions		X								
Alcohol Questionnaires										
Dependence—AUDIT			X							
Motives—DMQ		X								
Marijuana Questionnaires										
Expectancies—MEEQ			X					X		
Dependence—CUDIT-R			X							
Problems—MPS			X							
Craving—MCQ-SF			X	X	X	X	X	X	X	
Withdrawal—CWS			X	X	X	X	X	X	X	

Motives—MMM			X								
Tobacco Questionnaires											
Dependence—mFTQ			X					X			
Other Questionnaires											
Sexual History		X									
Exercise – GLTEQ			X		X	X	X	X	X		
Questions About Eating Behaviors			X		X	X	X	X	X		
School Engagement Questionnaire			X		X	X	X	X	X		
School History Questionnaire		X									
Sleep—PSQI			X		X	X	X	X	X		
Puberty History		X									
Puberty Stage – Tanner Scale		X									
COVID-19 Risk Perception and Coping Questions		X									
Interviews											
MINI 7.0 Adult, MINI 7.0 Kid		X									
TLFB		X	X	X	X	X	X	X	X	X	
Debriefing Interview									X		
Cognitive Tests											
CANTAB			X		X	X	X	X	X		
WTAR (18-25yrs, older adolescents)		X									
WASI (10-19 yrs, school cohort)		X									
MRI Tasks											X
Urinanalysis Tests											
Toxicology			X	X	X	X	X	X	X		X
Pregnancy											X

### **College-Aged Study Component:**

All study procedures will be identical to those proposed for the school-aged cohorts. The only exceptions to this are that: 1) all older adolescent participants will be regular cannabis users, 2) all protocol procedures will be conducted at MGH, and 3) since this group is not comprised of minors, all participants will be able to give consent to participating (i.e. no parental consent is required).

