### **III. SUBJECT SELECTION**

#### **Inclusion Criteria for School-Aged Study Component**

##### **General:**

1. Male and female children and adolescents from the Boston area who are between the ages of 10 and 19 (inclusive);
2. Have a parent or legal guardian who is able and willing to provide written informed consent for the active study phase (if under the age of 18);
3. Competent and willing to provide written informed assent for the active study phase (if under the age of 18);
4. Competent and able to provide written informed consent (if age 18 or older)
5. Able to communicate in English language
6. Able to commit to 9 study visits in approximately 60 days
7. No severe developmental delays (including, but not limited to, Autism Spectrum Disorder, Intellectual Disability, and Down Syndrome).
8. Able to safely participate in the protocol and appropriate for outpatient level of care, in the opinion of the investigator

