##### **Non-Using Group:**

1. Use of cannabis less than 5 times in lifetime
2. No cannabis use in the past year
3. No cannabis use before age 16

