#### **Inclusion Criteria for College-Aged Study Component**

##### **General:**

1. Male and female children and adolescents who are between the ages of 18 and 25 (inclusive) who report regular cannabis use
2. Competent and willing to provide written informed consent
3. Able to communicate in English Language
4. Cannabis use reported within 7 days of second baseline visit.

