**IV. SUBJECT ENROLLMENT**

Given the community-based nature of this protocol, specific enrollment procedures are tailored to the request of administrators from each individual school-district. For example, Westford administrators prefer that all students be initially screened under passive parental consent, prior to parents being contacted for full study consent. Our study-wide enrollment target is 500, with 100 older adolescent participants from the college-aged component and 400 school-aged children and adolescents from the school-aged component.

**School-Aged Study Component (The Epiphany School and Cohasset, Maynard, Northshore, Needham, Millis, Medford, Walpole, Westford, Cambridge, and Waltham Public Schools; Community):**

We aim to enroll 400 school-aged children and adolescents into the proposed protocol, including approximately 300 cannabis users and 100 non-using controls.

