deviation of the outcome pooling over groups during the baseline visit. In other words, we normalized the contrast of interest by the baseline variation in the outcome.

Secondary analyses

We conducted the following secondary analyses:

1. We tested our assumption of an additive model by fitting a model that includes a group by time interaction (i.e., the product of the contrast between CB-Abst and CB-Mon and the linear time trend variable). We conducted an omnibus test comparing the simpler additive model to the more complex interaction model – if the associated Wald test is significant at $p < \alpha_M$ (i.e., the specified level of significance α for a given module M) this will indicate the presence of a group by time interaction. Post-hoc comparisons of the regression coefficients of the interaction model will also indicate, if abstinence was associated with improvements in cognitive performance, when such improvement occurred. This secondary analysis addresses the second research question of the study.
2. We examined how cognitive performance of the two groups of cannabis users (the contingency management and monitoring groups) also compares against the control sample of non-users. This secondary analysis addresses the third research question of the study. We therefore...
 - a. Analyzed data from all three groups.
 - b. Created two dummy-coded variables to represent the 3 levels (contingency management, monitoring, and non-users) for group status. We used the non-user group as the referent, and had separate variables for the CB-Abst and CB-Mon groups.
 - c. Assessed (1) an additive model (main effects for group and time), and (2) an interaction model (also including at the group x time interaction in addition to the main effects).

- d. Conducted an omnibus test comparing the simpler additive model to the more complex interaction model – if the associated Wald test is significant at $p < \alpha_M$ (i.e., the specified level of significance α for a given module M), this will indicate the presence of a group by time interaction.
- e. If a group by time interaction or a main effect of group was found, we ran post-hoc comparisons to examine (a) if the CB-Mon group had worse performance compared to the non-user group, (b) if the CB-Abst group did not differ compared to the non-user group or (c) if performance for the CB-Abst group improved to levels matching the non-user group.

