3. We checked whether our conclusions were robust to the inclusion of covariates, examining the inclusion of age, CUDIT-R scores, and biological sex, all assessed at baseline. All covariates were converted into z-scores.
4. We checked whether our conclusions for our primary analysis were robust to our treatment of missing data (i.e., imputation of missing values). We reran the primary analysis using only observed values (we excluded values that were imputed).

Secondary Outcomes

The 2 secondary outcomes for the study were measures taken from the module in the set included in the study that CANTAB designated for assessing the domain of attention (see <https://www.cambridgecognition.com/cantab/cognitive-tests/attention>). While the MOT module is included in this list, as noted before since it is intended primarily for calibration and training, we excluded it from analyses.

CANTAB tasks

The module for assessment of attention was...

1. The Rapid Visual Information Processing (RVP) module.

Description: Subjects saw a sequence of digits appear one at a time in the center of the screen, at the rate of 100 digits per minute. The goal of the task was to indicate as quickly as possible when a target sequence of digits (e.g., 2-4-6) appeared onscreen. There were 54 3-digit target sequences, and 546 single-digit distractors.

Selection of outcomes

Again, for the RVP module we only analyzed the subset of recommended outcomes per CANTAB's manual (Cambridge Cognition, 2021). However, the CANTAB recommends both a measure of discriminability, A' , using signal detection theory (SDT), along with the proportion of false alarms. Because A' is calculated using the proportion of hits and false alarms, we excluded the proportion of false alarms due to redundancy issues. Therefore, there were a total of 2 recommended outcomes, listed below with a brief description and details on the units of measurement, range, and interpretation.

1. Outcomes to assess change in attention functioning:

- 1.1. A measure of discriminability, A' from the RVP module.

- A transformation of the proportion of hits and false alarms, providing an estimate of a subject's ability to detect the target sequences of digits after controlling for

response bias (i.e., biases to respond or not respond irrespective of the stimuli on screen).

- Bounded continuous variable, ranging from 0 to 1, where higher scores indicate a greater ability to discriminate between targets and distractors.

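### The SAP's comparison with non-users has no age term, so the answer on return to non-user levels may be confounded by age

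*Protocol*

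**What the plan says.** **Who is enrolled.** The Protocol's general inclusion criteria for the school-aged component take participants "between the ages of 10 and 19 (inclusive"). Section IV sets that component at 400, "including approximately 300 cannabis users and 100 non-using controls". The criteria for the Non-Using Group, such as "Use of cannabis less than 5 times in lifetime", concern cannabis history only. No age or sex matching is described. The college-aged component takes people "between the ages of 18 and 25 (inclusive) who report regular cannabis use", and Section V states that "all older adolescent participants will be regular cannabis users". All non-users therefore come from the 10-19 component.

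**What is analysed.** The SAP is titled for high-school-aged adolescents and plans 70 non-users, 70 CB-Abst and 70 CB-Mon. It gives no age range and does not mention the college-aged component. Its third research question is whether performance under abstinence returns to the level of non-using peers. Secondary analysis 2 answers it in all three groups: "Assessed (1) an additive model (main effects for group and time"), followed by an interaction model that adds group by time. Age is not listed.

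**Where age appears.** Secondary analysis 3 checks whether conclusions are robust, "examining the inclusion of age, CUDIT-R scores, and biological sex, all assessed at baseline". It does not say which models it covers. The Protocol's own three-group analysis (Section VI) controls for relevant covariates but names none.

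**The concern.** Randomisation protects CB-Abst versus CB-Mon. It does not protect either group's comparison with non-users, where age is a plausible confounder on the Protocol's own evidence. Section I.A reports ever-use of 10.3% in middle school, 30.1% in 9th grade and 48.6% in 12th grade, so unmatched users are likely to be older than non-users. Sections I.B and V say that the brain systems behind these tasks are still maturing through adolescence, so age is likely to relate to the scores.

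The direction matters. If scores improve with age, older users look closer to younger non-users than they should. Secondary analysis 2 treats an absence of difference between CB-Abst and non-users as a finding, so a bias that hides a deficit leads straight to the favourable conclusion of recovery.

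Secondary analysis 3 does not clearly repair this. If it does not reach the three-group model, age is never adjusted for there. If it does, CUDIT-R comes in with age. That scale scores problematic cannabis use, should be near zero in people who meet the non-user criteria, and so largely encodes user status. Adjusting for it removes part of the difference being estimated.

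**Working it through.** **1. Enrolment.** Protocol: 300 + 100 = 400 school-aged, plus 100 college-aged = 500, as stated. SAP: 70 + 70 + 70 = 210, as stated. On Protocol numbers, college-aged users are 100/(300 + 100) = 25% of all users. If the SAP set is high-school-aged only, as its title suggests, that share is 0%.

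**2. Age gap within high school.** Inputs: 30.1% ever-use in 9th grade and 48.6% in 12th. Assumptions: linear interpolation (36.3% in 10th, 42.4% in 11th), equal grade sizes, and ever-use as a proxy for weekly use.
- Mean grade of ever-users: (9×30.1 + 10×36.3 + 11×42.4 + 12×48.6)/157.4 = 10.70
- Mean grade of never-users: (9×69.9 + 10×63.7 + 11×57.6 + 12×51.4)/242.6 = 10.37
- Gap: about 0.32 years

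Adding grades 6-8 at 10.3% each widens the gap to about 1.5 years (10.09 versus 8.60). The Protocol recruits from 5th grade, but the SAP names high-school age.

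**3. Age gap if college-aged users are pooled.** Gap = 0.25 × (college mean age − school mean age). The mean ages are assumptions. For 17 and 20 years: 0.25 × 3 = 0.75 years. For 14.5 and 21.5 years: 0.25 × 7 = 1.75 years.

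**4. Bias.** Bias in SD = gap × gradient. The gradient is assumed to be 0.05-0.15 SD per year. With a baseline score in the model, bias becomes gap × gradient × (1 − r), with r = 0.6-0.75 from the Protocol's power paragraph, taking the age effect as equal at baseline and follow-up.

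| Analysis set | Gap (years) | Bias, no baseline score | Bias, with baseline score |
|---|---|---|---|
| High school only | 0.32 | 0.02-0.05 SD | 0.004-0.02 SD |
| College-aged users pooled | 0.75-1.75 | 0.04-0.26 SD | 0.01-0.11 SD |

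The pooled row shows only the gap that pooling creates. Any gap within ages 10-19 would come on top.

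**5. What such a bias does.** Illustration: two groups of 70, one time point, two-sided α = 0.05, no baseline score. SE = √(2/70) = 0.169 SD. Difference detectable with 80% power = (1.96 + 0.84) × 0.169 = 0.47 SD.

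Power to see a true 0.47 SD deficit, when age bias offsets part of it:
- bias 0.02 SD: 77%
- bias 0.05 SD: 71%
- bias 0.04 SD: 73%
- bias 0.26 SD: 24%

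With no true difference, the rejection rate in the pooled case is 5.6%-34% instead of 5%. With a baseline score it is 5.1%-12%.

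**6. CUDIT-R in the three-group model.** Take non-users at 0, users with mean d and SD s, equal groups of n, and residual variance unchanged. The variance of the CB-Abst versus non-user contrast goes from 2σ²/n to σ²[2/n + d²/(2ns²)], a ratio of 1 + d²/(4s²). Assumed d and s: 8 and 4 give 2.0; 12 and 6 give 2.0; 15 and 6 give 2.6. The covariate roughly doubles the variance or worse, and it changes what the contrast means.

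**The case against.** **Age is in the plan.** The SAP's Covariates section commits to age and sex as a minimum for robustness. Secondary analysis 4 is limited in words to the primary analysis and analysis 3 is not, which favours reading analysis 3 as reaching the three-group model. This stands in part: a claim that age is absent from the SAP would be wrong. But the reach is inferred, age has only a supporting role, and no version with age but without CUDIT-R is specified for this comparison.

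**The additive model may already adjust for the baseline score.** The Covariates section describes it that way, and analysis 2 reuses the term. If the score is carried over, the bias shrinks as in step 4. This stands as a limit on size. Analysis 2 does not restate the covariate, however, and conditioning on baseline moves the question from absolute levels, which research question 3 asks about, towards conditional change.

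**The analysis set.** A reader might infer that users up to 25 are compared with controls up to 19. The documents do not establish this. The SAP's title and its 70/70/70 plan point to a high-school sample. Its list of published papers on study data includes one on adolescent and young adult users, which leaves the matter open without settling it.

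**The inputs are assumed.** They are. The high-school ever-use figures alone give only about a third of a year.

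**Conclusion.** The gap in the plan is real: a non-randomised, non-age-matched comparison that answers one of three stated research questions has no age term in its listed models, and the only age adjustment is of unclear reach and tied to CUDIT-R. The supported conclusion is that the answer may be confounded by age. A reader might go further and say that it is confounded; the documents do not show this, because they give no ages by group and no age gradient.

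The size cannot be derived from the documents. On the assumptions above it runs from negligible (about 0.02-0.05 SD, high school only) to material (up to about 0.26 SD, college-aged users pooled without a baseline score). Which end applies turns mainly on an analysis set that the SAP does not define.

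The key confirmatory effect, CB-Abst versus CB-Mon, is randomised and is not affected.

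**What to change.** 1. State the age range of the SAP analysis set and whether college-aged participants are in it.
2. In secondary analysis 2, enter baseline age and sex, without CUDIT-R, in both the additive and the interaction model, as the main version of the non-user comparison. State whether the baseline score is also included.
3. Restrict that comparison to ages 10-19, where non-users were enrolled. Above 19, age adjustment would be extrapolation.
4. Confine the CUDIT-R adjustment in secondary analysis 3 to the models that contain users only.
5. Report age by group.

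**Cost.** Two covariates already collected, SAP wording and a re-run. Any users aged 20-25 leave this comparison only. The SAP dates its unblinded analysis to 02/03/2023, so the change must be labelled as made after unblinding, as the SAP already does for its added recall outcome.
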